5.3.1. Circulating Tumor Cells (CTC) enumeration in blood

For all samples collected for each patient, circulating tumor cells identified by a combination of morphology and/or diagnostic staining characteristics will be enumerated as a simple count of circulating tumor cells per milliliter of peripheral blood.

5.3.2. *PDGFR α and PDGFR β protein expression in tumor tissue*

PDGFR α and PDGFR β protein expression will be assessed by immunohistochemical staining interpreted by a pathologist experienced in interpreting these assays. Separate assays will be used for each receptor. Results of both assays will be reported as qualitatively positive or negative based on analytically validated criteria for interpretation of each assay's protein expression score.

5.3.3. *PDGF-A, B, C, and D canonical ligand expression in tumor tissue*

PDGF-A, B, C and D ligand expression will be assayed by real-time RT-PCR with relative quantification to housekeeping genes MRPL19, SF3A1 and PPIA. Normalized relative expression data will be reported using the Ct value of the gene of interest (GOI) and average Ct of the reference genes for that sample (RG) transformed with the following formula: $2^{-(20-GOI+RG)/1000}$. Additional approaches for normalizing and reporting relative gene expressions may be explored as deemed appropriate.

5.3.4. *Safety Variables*

Safety measures that will be used in the study include adverse events (AEs), DLT, clinical laboratory test results, vital signs, electrocardiograms (ECGs) and ECHO/MUGA scanning.

Adverse event-related variables are listed below:

- **Adverse event (AE)** is defined as any untoward medical occurrence in a patient administered a pharmaceutical product, without regard to the possibility of a causal relationship.
- **AEs of special interest (AESIs)**

AESI for olaratumab:

- Infusion-related reactions (IRRs)

AESI for combination of olaratumab and doxorubicin:

- Cardiac arrhythmias and cardiac dysfunction

Notes: Categories of AESI may be modified as the understanding of the safety of the investigational drug increases. The final list of categories will be maintained at both compound and study level and reported in the clinical study report (CSR).

- **Consolidated AEs** are composite AE terms consisting of synonymous Medical Dictionary for Regulatory Activities (MedDRA) preferred terms (PTs) to allow meaningful interpretation of the AE data. Consolidated AE categories and PTs will be maintained at compound level and reported in the CSR.
- **Serious adverse event (SAE)** is any AE that results in one of the following outcomes:

- death
 - a life-threatening experience (that is, immediate risk of dying)
 - persistent or significant disability/incapacity
 - initial or prolonged in-patient hospitalization
 - congenital anomaly/birth defect
 - considered significant by the investigator for any other reason
- **Treatment-emergent adverse event (TEAE)** is defined as an event that first occurred or worsened in severity after baseline and 30 days after the last dose of study treatment and related SAEs reported beyond 30 days after the last dose of study treatment, where last dose stands for actual dose, that is, 0 dose is not counted as last dose.

Exposure-related variables are listed below:

- **Dose exposures:** As reported in the eCRF
- **Number of dose level reductions:** Sum of the number of dose level reductions as reported in the eCRF
- **Dose delays:** As reported in the eCRF
- **Dose withheld/skip (Not Administered):** As reported in the eCRF
- **Dose interruption:** As reported in the eCRF

5.3.5. *Efficacy Variables*

The study was not designed to make an efficacy assessment. However, any tumor response data will be tabulated according to assigned treatment.

Circulating tumor cells (CTC) will be assessed at pre-olaratumab and post-olaratumab in whole blood.

Secondary efficacy analysis will be performed to investigate antitumor activity by assigned treatment. Response and disease progression will be evaluated using Response Evaluation Criteria in Solid Tumors (RECIST) version 1.1 (Eisenhauer et al. 2009) for all tumors.

Overall Response Rate (ORR) is defined as the percentage of patients achieving a best overall response of either Complete Response (CR), complete responses unconfirmed (CRus) or Partial Response (PR), as determined by RECIST 1.1. The best overall response is the best response from the start of the treatment until PD/recurrence.

Disease control rate (DCR) is defined as the percentage of patients achieving a best overall response of CR, CRu, PR, or SD as determined by RECIST 1.1. Patients who do not have any

postbaseline tumor response assessments for any reason are considered non-responders and are included in the denominator when calculating the response rate.

Progression-free survival (PFS) is defined as the time from the date of first study dose to the first date of radiologic disease progression or death due to any cause. [Table JGDM.5.1](#) defines the rules of censoring to be applied to PFS.

3-month Progression-free survival (PFS) is defined as the 3-month PFS rate as estimated using Kaplan-Meier methods. PFS is as defined above.

Rate of Resection is defined to be the percentage of patients whose tumors are determined to be resectable divided by the total number of patients. The evaluation of resectability of a tumor is determined by the surgeon in consultation with the multi-disciplinary team, and depends on the tumor stage and the patient's co-morbidity. The primary aim of surgery is to completely excise the tumor with a margin of normal tissue.

Table JGDM.5.1. Censoring Rule of PFS Primary Analysis

Situation	Event / Censor ^d	Date of Event or Censor ^e
Tumor progression^a or death	Event	Earliest date of PD or death
No tumor progression and no death	Censored	Date of last adequate radiological assessment or date of first study dose
unless		
No baseline radiological tumor assessment available	Censored	Date of first study dose
No adequate^b postbaseline radiological tumor assessment available and death reported after 2 scan intervals ^c following first study dose	Censored	Date of first study dose
New anticancer treatment (including surgery) started and no tumor progression or death within 14 days	Censored	Date of adequate radiological assessment prior to (start of new therapy +14 days) or date of first study dose (whichever is later)
Tumor progression or death documented immediately after 2 or more consecutive missing scan intervals following last adequate radiological tumor assessment or first study dose (whichever is later)	Censored	Date of last adequate radiological assessment prior to the missing assessment or date of first study dose

Abbreviations: CR = complete response; PD = progressive disease; PFS = progression free survival; PR = partial response; SD = stable disease.

- a Symptomatic deteriorations (that is, symptomatic progressions, which are not radiologically confirmed) will not be considered as disease progressions.
- b Adequate radiological tumor assessment refers to an assessment with one of the following responses: CR, PR, SD, or PD.
- c The 2-scan interval is counted from the date of last adequate tumor assessment to the date of next 2 scheduled tumor assessments plus 14 days (adjusted by tumor assessment window).
- d Refer to flow chart in [Appendix 1](#) if a patient meets multiple censoring criteria.
- e If there are multiple dates associated with 1 assessment, the assessment date will be set to the first date when the overall response is PD and the last date otherwise.

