4.3. Exploratory Objectives

The exploratory objectives of this study are:

- to evaluate blood, CTCs, and tumor tissue pre- and post-therapy for biomarkers related to pathways associated with STS, the mechanism of action (MOA) of olatumab, cancer-related conditions, and/or immune cells/immune and tumor microenvironment functioning within the disease state and/or cancer-related conditions.
- to assess the relationship between biomarker expression at baseline, and change from baseline, and clinical outcomes.

5. A Priori Statistical Methods

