5.2. General Considerations

Statistical analysis of this study will be the responsibility of Eli Lilly and Company (Lilly). The analyses for this study will be descriptive, except for possible exploratory analysis as deemed

appropriate. Data analyses will be provided by cycle (cycle 1 versus cycle 2 onward) for specified analyses and for all study patients combined wherever appropriate. For continuous variables, summary statistics will include number of patients, mean, median, standard deviation, minimum, and maximum. Categorical endpoints will be summarized using number of patients, frequency, and percentages. Unless otherwise specified, missing data will not be imputed.

The interpretation of the study results will be the responsibility of the investigator with the Lilly Clinical Research Physician (CRP)/Clinical Research Scientist (CRS), pharmacokineticist, and statistician. The CRP or CRS and statistician will also be responsible for the appropriate conduct of an internal review for both the final study report and any study-related material to be authorized by Lilly for publication.

Exploratory analyses of the data not described below will be conducted as deemed appropriate.

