5.9. Biomarker Analyses

The primary endpoints of the study are

- CTC enumeration changes pre- and post-olatumab monotherapy in whole blood
- PDGFR α and PDGFR β and canonical ligands (PDGF-A, B, C, and D) expression changes pre- and post-olatumab monotherapy in tumor tissue

The percent change from baseline for post-olatumab monotherapy in biomarker expressions will be provided for each patient and summarized for all qualified patients in the BE1 population. For patients with an observed value of 0 for baseline expression or both baseline and post-olatumab monotherapy expressions, a value of 0.1 will be used. In particular, summary of number and frequency of patients with at least 30% reduction in change from baseline PDGFR α expression will be provided.

Exploratory biomarker analyses may be described in a separate biomarker statistical analysis plan, if deemed necessary.

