5.14. Interim Analysis

With limited prior experience with the performance of the biomarker assays (i.e, QC issues, dynamic range, data variability), an interim analysis will be done to evaluate the biomarker data once approximately half of the evaluable patients complete the second tumor tissue biopsy and C2D1 whole blood draw. The purpose of this interim analysis is to review the biomarker data in order to identify technical issues that may potentially impact the study's ability to meet its key objectives. If this interim look at the biomarker data warrants any changes in the study conduct, it will be implemented in an appropriate manner (that is, protocol amendment). At this interim analysis, a review of the safety data will also be conducted.

This would be in addition to the safety data review that will be conducted after 5 patients have completed 2 cycles of treatment.

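### Applied as printed, the Ct formula in SAP 5.3.3 makes reported PDGF-ligand expression rise when transcript falls, so the minus sign must be confirmed or corrected

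*SAP*

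**What the plan says.** SAP 5.3.3 assays the four ligands by real-time RT-PCR relative to three housekeeping genes. "Normalized relative expression data will be reported using the Ct value" of the target gene and the mean of the reference genes; the two symbols are defined as the "Ct value of the gene of interest (GOI) and average Ct of the reference genes" in the same sample. The transformation is printed as "2^{-(20-GOI+RG)/1000", with a brace closing the superscript after 1000. The section adds that other normalisations may be explored, but specifies none.

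SAP 5.9 names as part of a primary endpoint "canonical ligands (PDGF-A, B, C, and D) expression changes pre- and" post-olaratumab monotherapy. The percent change from baseline "in biomarker expressions will be provided for each patient and summarized for all qualified patients" in the BE1 population. One exploratory objective in SAP 4.3 is "to assess the relationship between biomarker expression at baseline, and change from baseline, and clinical outcomes".

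The protocol gives no formula for the ligands. Neither document gives a worked value, says that larger values mean less expression, or reverses the sign at a later step.

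**The concern.** In real-time PCR, Ct is the cycle at which the signal crosses a threshold, so more transcript gives a lower Ct. The documents do not say this; it is a general property of the assay they name. A quantity labelled relative expression should therefore fall as GOI rises. The bracket (20 − GOI + RG) already does that, because GOI enters with a negative sign. The leading minus negates it again and turns the scale round.

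If someone programs the formula literally, a fall in ligand after olaratumab is tabulated as a rise, for each patient and in the summary of a primary endpoint. The exploratory associations of ligand expression and change with clinical outcome would also point the wrong way.

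A second, separate question is where the superscript ends. With the division by 1000 inside the exponent, the scale has almost no range.

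**Working it through.** **Inputs.** From SAP 5.3.3: the printed formula, and GOI and RG as Ct values. Assumed, because the documents give no figure: amplification efficiency of 100% (one cycle per doubling), then varied from 80% to 110%. The plan states no result from this formula, so there is no figure to reproduce.

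**Step 1: rewrite the exponent.** −(20 − GOI + RG)/1000 = (GOI − RG − 20)/1000. It increases with GOI.

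**Step 2: percent change.** Let d be the change in (GOI − RG) from baseline to post-monotherapy. At 100% efficiency the true ratio is 2^(−d), so a halving has d = 1 and a 30% fall has d = −log2(0.7) = 0.5146. The constant 20 cancels in the ratio, as does 1000 when it lies outside the exponent.

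| Reading of the formula | Reported ratio | True halving reads | True 30% fall reads |
|---|---|---|---|
| As printed (minus kept, /1000 inside exponent) | 2^(d/1000) | +0.069% | +0.036% |
| Minus kept, /1000 outside | 2^d | +100% | +42.9% |
| Minus removed, /1000 inside | 2^(−d/1000) | −0.069% | −0.036% |
| Minus removed, /1000 outside | 2^(−d) | −50% | −30% |

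The sign depends only on the minus, and the size only on where the superscript ends. Only the last row returns the true change. In the second row the reported ratio is the reciprocal of the true ratio, so reversing the sign of a tabulated percent change would not repair it.

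**Step 3: vary the efficiency.** At efficiency E a halving has d = ln 2 / ln(1 + E).

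| E | d | As printed | Minus kept, /1000 outside |
|---|---|---|---|
| 0.8 | 1.179 | +0.082% | +126.5% |
| 0.9 | 1.080 | +0.075% | +111.4% |
| 1.0 | 1.000 | +0.069% | +100% |
| 1.1 | 0.934 | +0.065% | +91.1% |

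The sign is wrong throughout.

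**Step 4: levels at illustrative values of GOI − RG.**

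| GOI − RG | As printed | Minus kept, /1000 outside | Minus removed, /1000 outside |
|---|---|---|---|
| 0 | 0.98623 | 9.5 × 10⁻¹⁰ | 1,048.6 |
| 5 | 0.98966 | 3.1 × 10⁻⁸ | 32.8 |
| 15 | 0.99654 | 3.1 × 10⁻⁵ | 0.032 |

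As printed, 15 cycles move the value by 0.99654/0.98623 − 1, about 1.05%. The constants 20 and 1000 give convenient numbers only in the last column, which suggests that it is the intended form.

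**The case against.** The strongest objection is that everything rests on one superscript in text extracted from a PDF. That text has other character-level faults: the drug name is misspelled in several places, and the imaging window in Protocol 6.2 appears once with a less-than sign and elsewhere as plus or minus 7 days. The minus may be such a fault. Nothing in the two documents can settle this, so the point stays conditional and the first action is a source check.

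Next, the literal formula would show almost no change in any patient, which looks broken rather than misleading. A credible but false +100% requires the minus to be real and the division by 1000 to be misplaced. That is fair. But whoever notices the compressed scale and moves the 1000 out of the exponent, leaving the minus, arrives at exactly that reading.

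The interim biomarker review in SAP 5.14 is prompted by limited experience with assay matters such as "QC issues, dynamic range, data variability". It would probably reveal a collapsed range. It need not reveal a reversed sign, because no direction is specified for the ligands and inverted values can have a plausible spread.

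Protocol 9.2.2 has laboratory data transferred from vendor databases, so the laboratory may apply a correct transformation itself. The SAP does not say who applies it. If the laboratory does so correctly, results are unaffected.

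Finally, the stakes are limited. SAP 5.2 says "The analyses for this study will be descriptive", apart from possible exploratory work, and no test or decision rule uses the ligands. This bounds the severity but does not remove the error.

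**Conclusion.** The concern holds as a conditional statement: applied as printed, the formula gives the ligand percent changes the wrong sign, wherever the division by 1000 sits. This needs only that Ct falls as transcript rises. The sizes, +0.069% or +100% for a true −50%, also assume 100% efficiency; between 80% and 110% the sign does not change.

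It should be fixed, with medium confidence, because the minus has not been verified in the source and the laboratory may already supply correctly directed values. The effect is confined to the ligand part of the primary endpoint and the exploratory analyses built on it. CTC counts, PDGFRα and PDGFRβ, the 30% reduction rate for PDGFRα and the sample-size rationale do not use this formula.

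**What to change.** 1. Check the minus sign and the end of the superscript against the source SAP and the laboratory specification.
2. If the minus is confirmed, restate the formula in SAP 5.3.3 with explicit brackets, for example [2^(20 − GOI + RG)]/1000. If only the end of the superscript is unclear, bracket it in the same way. In this form both constants cancel in percent or fold change, though not in absolute change. Log2 fold change, −(post ΔCt − baseline ΔCt) with ΔCt = GOI − RG, is an optional alternative scale.
3. State in SAP 5.3.3 whether the laboratory or the sponsor applies the transformation.
4. Before the interim biomarker review, add a programming check that raising GOI by one cycle with RG fixed halves the reported value. This tests both the sign and the placement of 1000.

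The cost is one source check, a one-line correction if the minus is confirmed, a sentence on who applies the transformation, and one programming check. Sample size, visits and samples do not change.

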- **Olaratumab Monotherapy Treatment Period:** begins at the first administration of olaratumab 20 mg/kg on Day 1 of Cycle 1 and ends on Day 21 of Cycle 1.
- **Combination Olaratumab plus Doxorubicin Therapy Treatment Period:** begins after the post Cycle 1 treatment biopsy is obtained, with the first administration of olaratumab 20 mg/kg and doxorubicin 75 mg/m² on Day 1 of Cycle 2, followed by the administration of olaratumab 20 mg/kg on Day 8 of Cycle 2. This treatment period continues from Cycle 3 through Cycle 7 with the administration of olaratumab at a dose of 15 mg/kg on Days 1 and 8 and doxorubicin 75 mg/m² on Day 1 of each 21-day cycle. Upon completion of the combination therapy treatment period, the patient will no longer receive study treatment.
- **Post-discontinuation Follow-Up:** begins the day after the patient and the investigator agree that the patient will no longer continue study treatment.
 - **Short-term follow-up:** begins the day after the patient and the investigator agree that the patient will no longer continue study treatment and lasts approximately 30 days (±7 days). The short-term follow-up visit occurs at or near the end of the short-term follow-up period (±7 days).
 - Follow-up for safety - Patients who undergo surgical resection will be followed for safety for approximately 30 days (±7 days) after surgery.
 - **Long-term follow-up:** begins the day after short-term follow-up is completed.
 - Follow-up for progression - Patients who discontinue study treatment, or have completed 6 cycles of combination therapy, and have not progressed and have not initiated a new systemic treatment for their disease will be assessed for progression by imaging studies every 6 weeks (<7 days) until PD. Patients who have had surgical resection will not be followed for subsequent progression by imaging studies.

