8.1.2.2.2. On Study Treatment

All AEs and SAEs, regardless of relatedness to study drugs or protocol procedures, occurring while the patient is receiving study drug must be reported to Lilly or its designee. A patient is

considered to be receiving study drug from the time he/she receives the first dose of study drug to when he/she receives the last dose of study drug.

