8.1.2.2.3. Follow-Up Visit

All AEs and SAEs, regardless of relatedness to study drugs or protocol procedures, occurring during the follow-up visit (Visit 801) must be reported to Lilly or its designee. The follow-up visit begins the day after the patient and the investigator agree that the patient will no longer continue study treatment. At the end of the follow-up visit, the patient will be required to have specific safety assessments ([Attachment 1](#)). The timing of these safety assessments is 30 ± 7 days after the last dose of study drug.

Following the safety assessments, which mark the end of the follow-up visit (Visit 801), the patient will continue into long-term follow-up until disease progression. Any ongoing AE or SAE considered possibly related to study drug should be followed during the long-term follow-up. In this instance, the patient should be followed in subsequent follow-up visits (Visit 802, Visit 8XX) until the event is resolved, or is no longer considered to be drug-related, or becomes stable, or returns to baseline, a new treatment is initiated for the patient, or the patient dies or is lost to follow-up.

If it is deemed to be in the best interest of the patient to start a new anticancer treatment prior to the scheduled end of the follow-up visit, the follow-up visit duration may be shortened. In this case, the follow-up assessments should be completed prior to the initiation of the new therapy.

After the follow-up visit (Visit 801), AEs are not required to be reported unless the investigator feels the AEs were related to either study drug, drug delivery system, or a protocol procedure. If an investigator becomes aware of any SAEs believed to be related to protocol procedures or study drug, the investigator should report the SAE to the sponsor, and the SAE will be entered in the Lilly Safety System.

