10.4. Safety Analyses

All patients who receive at least 1 dose of study drug will be evaluated for safety and toxicity.

The safety and tolerability of study drug is determined by reported AEs, physical examinations, laboratory tests, ECGs, dose adjustments, and results from ECHO/MUGA scans.

All patients will be assessed regularly for potential occurrence of AEs from the time that the patient provides informed consent until 30 days after the last dose of study therapy. Adverse events will be summarized by MedDRA System Organ Class and preferred term, classified from verbatim terms. The incidence and percentage of patients with at least 1 occurrence of a

preferred term will be included, according to the most severe NCI-CTCAE Version 4.0 grade. The number of AEs reported per MedDRA preferred term will also be summarized. Causality (relationship to study drug) will be summarized separately. Duration of AE will be determined and included in listings along with action taken and outcome.

Laboratory results will be classified according to NCI-CTCAE Version 4.0. Incidence of laboratory abnormalities will be summarized; laboratory results not corresponding to an NCI-CTCAE Version 4.0 term will not be graded. Laboratory toxicity shifts from baseline to worst grade will also be provided.

The results from physical examination and vital sign measurement will be tabulated. Descriptive statistics will be provided as appropriate. Electrocardiogram and ECHO/MUGA evaluation will be listed.

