5.7. Concomitant Medications

The following concomitant medications used during study treatment period or up to the 30-day (± 7 days) postdiscontinuation follow-up period will be summarized by numbers and percentages by dose cohort, presented in decreasing frequency of the World Health Organisation drug term:

- all concomitant medications
- premedication for study drug

Patient listing of all concomitant therapies and premedications will be provided.

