5.11.3. Clinical Laboratory Evaluation

The severity of laboratory results will be classified according to CTCAE Version 4.0. The shifts in CTCAE toxicity grading from baseline to worst postbaseline (first dose up to 30 days after the last dose of study treatment) grade will be produced.

A patient listing of all laboratory data will be provided with a flag for values outside of the laboratory normal range.

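### The safety follow-up has two anchors in the protocol, and the SAP's last dose + 30 day cut-off has no ±7-day allowance, so required Visit 801 laboratory results and late AEs can miss the treatment-emergent and shift tables

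*SAP*

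**What the plan says.** **SAP windows.** Section 5.3.4 defines a TEAE as an event that "first occurred or worsened in severity after baseline and 30 days after the last dose of study treatment", counts the last dose as the last one actually given, and adds related SAEs reported later. I read this as a window that closes on day 30. Section 5.11.3 takes the worst post-baseline laboratory grade over "first dose up to 30 days after the last dose of study treatment". Neither section allows ±7 days. Section 5.7, for concomitant medications, runs "up to the 30-day (± 7 days) postdiscontinuation follow-up period".

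**Protocol, decision anchor.** Section 6.2 defines a short-term period that "begins the day after the patient and the investigator agree that the patient will no longer continue study treatment and lasts approximately 30 days", with a tolerance of ±7 days and the visit placed at or near its end. The Attachment 1 footnote repeats this, and Section 8.1.2.2.3 uses the same start. All AEs and SAEs in the period must be reported, whatever their cause (8.1.2.2.3, Table JGDM.5). Visit 801 includes hematology, chemistry, coagulation, urinalysis, ECG and ECHO/MUGA.

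**Protocol, last-dose anchor.** Section 8.1.2.2.3 goes on: "The timing of these safety assessments is 30 ± 7 days after the last dose of study drug". Section 10.4 has AEs assessed "until 30 days after the last dose of study therapy". Section 8.1.2.2.2 regards a patient as "considered to be receiving study drug from the time he/she receives the first dose of study drug to when he/she receives the last dose".

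**The concern.** Data that sites are required to collect should not leave the main safety tables merely because collection and analysis are timed from different dates. The last olaratumab dose of a full cycle is on Day 8 and the cycle lasts 21 days, so the decision to stop may come well after the last dose. A Visit 801 timed from the decision can then fall past the SAP cut-off.

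Three outputs are exposed:

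- **Laboratory shift table.** Visit 801 is the scheduled post-treatment laboratory visit, and its results can be excluded.
- **TEAE tables.** Late non-serious AEs and unrelated SAEs are reported by the site but not counted.
- **AESI summary and AESI listing.** Both are restricted to treatment-emergent events (SAP 5.11.2). A non-serious fall in ejection fraction first found at a late Visit 801 and reported as an AE would appear in neither.

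**Working it through.** The plan gives no figure to reproduce here; the check is date arithmetic.

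**Inputs**

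- SAP cut-off: day 30 after the last dose (5.3.4, 5.11.3).
- Visit 801 on the last-dose anchor: 30 ± 7 days after the last dose (protocol 8.1.2.2.3).
- Visit 801 on the decision anchor: 30 ± 7 days after the decision (protocol 6.2, Attachment 1).
- Last dose in a full cycle: olaratumab on Day 8 of 21 (protocol 6.2).
- Longest wait for recovery before mandatory discontinuation: 42 days from Day 1 (protocol 7.2.3.1).
- Gap g from last dose to decision: **assumption**, since the documents do not give it.

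**Gap scenarios**

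- Decision on the day of the last dose: g = 0.
- Decision when the next cycle would start: Day 22 − Day 8 = 14 days.
- Decision at the 42-day limit: Day 43 − Day 8 = 35 days.

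These assume that the Day 8 dose was given. If it was omitted and Day 1 was the last dose, the last two gaps each grow by 7 days.

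**Last-dose anchor.** Visit 801 falls on days 23 to 37, which is 15 permitted days. Days 31 to 37 lie past the cut-off: 7/15 = 47%. The target day 30 is inside.

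**Decision anchor.** Visit 801 falls g + 30 ± 7 days after the last dose.

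| Gap g | Visit 801, days after last dose | Permitted days past day 30 |
|---|---|---|
| 0 | 23–37 | 7 of 15 (47%) |
| 3 | 26–40 | 10 of 15 (67%) |
| 7 | 30–44 | 14 of 15 (93%) |
| 8 | 31–45 | 15 of 15 |
| 14 | 37–51 | 15 of 15 |
| 35 | 58–72 | 15 of 15 |

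The earliest permitted day is g + 23. It exceeds 30 once g is 8 or more, and from there every permitted visit is lost to the shift table. The percentages are shares of permitted days; they are shares of visits only if visits spread evenly over the window.

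**Stacked allowances.** Section 6.2 can be read as giving ±7 days to the period and another ±7 to the visit. With ±14 and g = 14 the range is days 30 to 58, and 28 of 29 days (97%) lie past day 30.

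**AE reporting tail.** On the decision anchor, mandatory reporting nominally ends g + 30 days after the last dose, so it runs g days past the SAP cut-off: 14 days at g = 14. Non-serious events and unrelated SAEs that first occur or worsen in that tail are collected but are not TEAEs.

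**Protocol against itself.** The two visit windows, 23 to 37 and g + 23 to g + 37, share a day only if g + 23 ≤ 37, that is g ≤ 14. For a longer gap no visit date meets both rules. At g = 35, a visit due on days 23 to 37 could fall due before the decision has been made.

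**The case against.** The case on the other side is substantial, and much of it stands.

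- **A reader might infer that the SAP contradicts the protocol.** It does not do so outright. Its last-dose anchor is the one in protocol 10.4 and in the timing sentence of 8.1.2.2.3. The conflict lies first inside the protocol; the SAP's own omission is the ±7 days.
- **A reader might infer that Visit 801 data usually fall outside the analysis.** *Usually* needs both the decision anchor and an assumed gap. Section 8.1.2.2.3 also lets follow-up be shortened before new anticancer treatment, which moves some visits earlier. *Outside the analysis* is too strong. The SAP lists all AEs, all SAEs and all laboratory data (5.11.2, 5.11.3), summarizes all deaths, keeps related SAEs as TEAEs, summarizes vital signs, ECG and ECHO/MUGA by time point without this cut (5.11.4), and gives registry SAE summaries regardless of treatment emergence (5.16).
- **A reader might infer that toxicity is understated, most of all after toxicity delays.** A shortened window can only lower a worst grade or leave it unchanged, so the direction is right, but the effect is not shown. A lost value matters only if it exceeds every earlier one, and evaluations continue at least every 21 (±3) days during a dose interruption (Attachment 1, footnote a).
- **A reader might infer a hole in AE collection** between the last dose, where 8.1.2.2.2 stops, and the decision, where 8.1.2.2.3 starts. Section 6.2 and Table JGDM.5 treat that interval as study treatment with all AEs reported, so this is a wording defect.
- **The SAP 5.7 window is not a contradiction.** Concomitant medications may have a different window from TEAEs.
- **A longer TEAE window has a price.** Resection is one of the listed reasons for stopping, and an open-ended window would bring in post-surgical events.

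What survives is that, on either anchor, some permitted Visit 801 dates fall past the SAP cut-off.

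**Conclusion.** The point holds in a limited form. The protocol gives short-term safety follow-up two anchors, and the SAP adopts one of them without the visit allowance. Required Visit 801 laboratory results can therefore miss the worst-grade shift table, and required AE reports can miss the TEAE and AESI outputs.

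On the last-dose anchor the exposure is 7 of 15 permitted days. On the decision anchor it is all of them from a gap of 8 days, taking a single ±7. The first figure needs no assumption about the gap. The second depends on a gap the documents do not state, for which 0 to 35 days is an illustrative range.

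The loss is confined to summary tables and treatment-emergent outputs. Whether it changes any toxicity estimate cannot be determined from the documents. The correction should be made because it stops required safety data from being dropped by rule, at little cost.

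**What to change.** **Protocol.** Reconcile Sections 6.2, 8.1.2.2.2, 8.1.2.2.3, 10.4 and Attachment 1 to one anchor for short-term follow-up and Visit 801, and make the on-treatment and follow-up reporting periods meet without an interval between them. Which date should time the visit is for the sponsor to settle.

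**SAP 5.3.4 and 5.11.3.** Extend the TEAE and laboratory windows to include Visit 801 and its ±7-day allowance, with related SAEs counted thereafter as now. This gives a bounded window: last dose + 37 days on the last-dose anchor, or decision date + 37 days on the decision anchor (last dose + 51 at a 14-day gap, + 72 at 35). Flag events that start after surgery or new anticancer therapy. Keep the strict last dose + 30 day tables as a sensitivity.

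**Cost.** Protocol and SAP wording, some programming, and no new visits or samples. On the decision anchor the window length will vary between patients, and some late events not due to treatment will be counted; the flags and the strict tables let a reader see how many.
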